Official title: Synergistic effect of ^{18}F -FDG PET radiomics and International Prognostic Index on outcome prediction in diffuse large B-cell lymphoma

NCT number: 04317313

Document date: July 29, 2021

Study Protocol and Statistical Analysis Plan

Background: Previous studies have shown that ¹⁸F-FDG PET radiomics is predictive of survival in DLBCL. However, to the best of the investigator's knowledge, a multi-feature radiomic signature for prognosis assessment of DLBCL has not yet been described. Furthermore, it remains unclear whether PET-based radiomics could add more prognostic values to the IPI in DLBCL.

Objectives: This study aims to develop ¹⁸F-FDG PET radiomic signatures, and investigate whether the RS could improve the prognostic value of the IPI in predicting progression-free survival (PFS) and overall survival (OS) in DLBCL.

Study design and methods:

Study population

We retrospectively included patients with newly-diagnosed DLBCL between July 2013 and July 2019 in our institution. The inclusion criteria were: 1) histopathologically confirmed DLBCL, 2) over 18 years old, 3) underwent pre-treatment ¹⁸F-FDG PET/CT, and 4) initial treatment with R-CHOP (rituximab, cyclophosphamide, doxorubicin, vincristine, and prednisone) or R-EPOCH (rituximab, etoposide, prednisone, vincristine, cyclophosphamide, and doxorubicin). Patients were excluded if they had coexistent central nervous system lymphoma or second primary cancer, underwent surgical resection, or had an incomplete follow-up.

Clinical variables including gender, age at diagnosis, cell of origin, performance status, B symptoms, Ann Arbor stage, serum lactate dehydrogenase level, serum β 2-microglobulin (β 2-MG) level, extranodal involvement and treatment regimens of each patient were recorded. The IPI score was calculated.

Patient Treatment and Follow-up

Patients were initially treated with standard first-line chemotherapy every 21 days. Response to treatment was assessed according to the Lugano classification.

Follow-up was performed every 3 months after the completion of treatment, and ended in July 2021. The endpoints included OS (defined as the period from the initial diagnosis to the death from any cause) and PFS (defined as the period from the initial diagnosis to the progression, relapse or death from any cause).

PET Image Segmentation and Feature Extraction

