PET images were analyzed by two experienced nuclear medicine physicians who were blind to the patients' outcome. The volumes of interest (VOIs) were semiautomatically delineated using the LIFEx software (<https://www.lifexsoft.org/index.php>) with a fixed threshold of 41% SUVmax. A total of 1245 radiomic features were extracted via PyRadiomics software. The radiomics features consisted of four groups: (1) first-order statistics features; (2) shape descriptors features; (3) texture features calculated by gray level co-occurrence matrix (GLCM), gray level dependence matrix (GLDM), gray level run length matrix (GLRLM), and gray level size zone matrix (GLSZM); (4) filter and wavelet features obtained by filter and wavelet transformation of the original image, such as exponential, logarithm, square, square root and eight frequency band combinations (low-high-low [LHL], low-high-high [LHH], high-low-low [HLL], low-low-high [LLH], high-low-high [HLH], high-high-high [HHH], high-high-low [HHL] and low-low-low [LLL]).

Radiomics feature selection

First, intra-class correlation coefficients (ICCs) were used to evaluate the inter- and intra-observer agreement for 1248 features, including 3 conventional and 1245 radiomics features. Features with both inter- and intra-observer ICCs greater than 0.75 were retained. Then, the least absolute shrinkage and selection operator (LASSO) Cox regression algorithm with 10-fold cross-validation was applied to select the optimal features with non-zero coefficients in the training set. The radiomics signature was developed by linear combination of the selected features weighted by their respective coefficients. The cut-off value of the radiomics signature was identified by X-tile software. Based on the cut-off value of the R-signature, patients were divided into high-

and low-risk groups. Survival function of the R-signature was estimated by Kaplan-Meier analysis, and survival distributions were compared using log-rank test.

Model construction

Univariate Cox regression analysis was performed to investigate the prognostic value of the R-signature and clinical variables. Then, all significant variables were enrolled into a stepwise multivariate Cox regression to build an integrated radiomics-based model for PFS and OS prediction.

Model performance assessment

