Time-dependent ROC curve analysis was conducted to investigate the predictive accuracy of the R-signature, clinical variables and the integrated radiomics-based model. The 95% confidence interval (CI) of the area under the curves (AUCs) were calculated by bootstrapping with 1000 resampling. The AUC between the radiomics-based model and clinical variables was compared by using the Delong's test. The calibration plots and the Hosmer-Lemeshow test were used to compare the predicted and observed probabilities of the radiomics-based model. The decision curve analysis (DCA) was applied to determine the clinical utility by quantifying the net benefits under different threshold probabilities in the whole cohort.

Statistical analysis

The chi-square test and independent *t*-test were performed using SPSS software (version 25.0, IBM). ICC, LASSO regression analysis, time-dependent ROC analysis, Delong's test, calibration plots, Hosmer-Lemeshow test, DCA and Kaplan-Meier survival analysis were performed using R software (version 3.6.1, <http://www.r-project.org>). A two-sided *P* value of < 0.05 was considered statistically significant.

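### The continuous radiomics signature is split in two at an X-tile cut and tested by log-rank on the groups, and the plan does not say whether the score or the high/low group enters the Cox, ROC, calibration and decision-curve steps

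*Combined protocol and SAP*

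**What the plan says.** The section Radiomics feature selection of the combined protocol and SAP defines a continuous quantity: "The radiomics signature was developed by linear combination of the selected features weighted by their respective coefficients". It then states "The cut-off value of the radiomics signature was identified by X-tile software", followed by "Based on the cut-off value of the R-signature, patients were divided into" a high-risk and a low-risk set. Kaplan-Meier curves are drawn and "survival distributions were compared using log-rank test".

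The next two sections go on using the signature by name. Model construction says "Univariate Cox regression analysis was performed to investigate the prognostic value of the R-signature and clinical variables", and significant variables pass to a stepwise model. Model performance assessment says "Time-dependent ROC curve analysis was conducted to investigate the predictive accuracy of the R-signature, clinical variables and the integrated radiomics-based model"; calibration and decision curves follow. None of these sentences says whether the score or the high/low group is used.

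On the comparator, the section Study population says only "The IPI score was calculated". Whether it is analysed as a score or as risk groups is not given. The documents also give no cut value, share of patients above the cut, data set in which the cut was found, sample size, event count or effect size.

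**The concern.** Splitting a continuous score treats all patients on one side of the cut as alike, and treats two patients just either side of it as different. If risk rises smoothly with the score, this discards information at any cut, including one fixed in advance.

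Two things are at stake. First, the only test tied by name to the signature before modelling is run on the grouped variable. Second, the study asks whether the signature adds to the IPI for PFS and OS, and the answer depends on the form in which the signature enters the models. Two analysts could follow the text faithfully, one entering the score and the other the group, and report different hazard ratios, AUCs, calibration plots and net-benefit curves.

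**Working it through.** The plan states no power or information figure, so there is nothing of its own to reproduce. The inputs from the documents are a continuous score, two groups and a two-sided 0.05 level. Everything else below is assumed.

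**1. Information kept by a fixed cut.** For a normal score with a log-linear effect of modest size, the efficiency of a two-group test relative to the continuous score is φ(c)² / [p(1 − p)], where p is the share above the cut c.

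| Split | φ(c) | Efficiency | Loss |
|---|---|---|---|
| 50:50 | 0.3989 | 0.1592 / 0.25 = 0.637 | 36% |
| 30:70 | 0.3477 | 0.1209 / 0.21 = 0.576 | 42% |
| 20:80 | 0.2800 | 0.0784 / 0.16 = 0.490 | 51% |

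**2. Dependence on the shape.** Under a linear effect, the loss at the best possible cut is 25% for a uniform score, 35% for an exponential, 19 to 25% for the bimodal shapes tried, and 50% for a Laplace. If the true effect is a step at the cut, the split loses nothing. With the step at the median of a normal score, it is the linear term that is inefficient (0.64). So 36% is not a general minimum.

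**3. What this means for power with a fixed cut.** Power = Φ(ln HR × √(events × efficiency) − 1.96). With 70 events and HR 1.4 per SD (both assumed; ln 1.4 = 0.3365):
- continuous: Φ(0.3365 × √70 − 1.96) = Φ(0.855) = 80%
- 50:50: Φ(0.3365 × √44.6 − 1.96) = Φ(0.286) = 61%
- 20:80: Φ(0.3365 × √34.3 − 1.96) = Φ(0.010) = 50%

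Events needed for 80% power are (1.96 + 0.842)² / [(ln HR)² × efficiency]. At HR 1.5 per SD that is 7.85 / 0.1644 = 48 for the continuous score and 48 / 0.637 = 75 for a median split. At HR 1.3 the figures are 115 and 180; at HR 2.0, 17 and 26.

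A simulation agrees (2,000 runs, N = 150, about 56 events, HR 1.5 per SD): power was 84% for the continuous score and 64% for a fixed median split.

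**4. Discrimination with a fixed cut.** The grouped AUC is (sensitivity + specificity) / 2. For equal-variance binormal scores, 30% events and a continuous AUC of 0.70:
- 50:50: (0.700 + 0.586) / 2 = 0.64
- 30:70: (0.487 + 0.780) / 2 = 0.63
- 20:80: (0.356 + 0.867) / 2 = 0.61

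Steps 3 and 4 do not describe the same signature. HR 1.4 per SD corresponds to an AUC of about 0.61, falling to 0.58 at a median split. An AUC of 0.70 needs HR of about 1.9 per SD, and with 70 events power there is above 99% for the continuous score and still 97 to 99% at a median split. A weak signature loses mainly power; a strong one loses mainly discrimination.

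**5. A cut searched in the same data.** The simulation in step 3 was repeated with the largest log-rank statistic taken over cuts from the 10th to the 90th percentile. At HR 1.5 per SD, the mean chi-square was 13.2 for the searched cut against 9.6 for the continuous score. With no true effect, the searched test rejected in about 38% of runs at a nominal 5%. In this setting grouping makes the signature look stronger, not weaker.

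**The case against.** The strongest reply is that the plan probably does keep the score continuous in its models. A cut-off of the R-signature makes sense only if the R-signature is the score, the grouped variable has its own label (high- and low-risk), and the Cox and ROC sentences name the R-signature. On that reading the split serves the Kaplan-Meier curves, the univariate Cox analysis already tests the score, and the main objective is addressed by the stepwise model and the AUC comparison, not by the log-rank test.

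Much of this stands. It is a reasonable reading, and the documents do not show that information is lost in the models. It is not the only reading: the same section also speaks of the survival function of the R-signature when it means the grouped curves, and the log-rank comparison is a formal test, not just a display.

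A reader might go further and infer that a two-level signature is set against a finer IPI, so that the estimated gain over the IPI must come out too small. The documents do not support that. They do not say that the group is carried forward, nor how the IPI is coded. If the group is carried forward in the data that chose the cut, step 5 shows its apparent strength can be inflated. A handicap would be expected only with a fixed cut or in independent data.

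**Conclusion.** The point holds as a cheap improvement. The plan groups a continuous signature for its log-rank test and leaves open which form enters the later steps. With a fixed cut, the loss is 36% at 50:50 and about 51% at 20:80, provided the score is normal and its effect log-linear. The documents supply none of these conditions; the loss differs for other shapes and vanishes for a step effect at the cut. The documents give no rationale for a step, and LASSO-Cox itself models the features log-linearly.

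No direction of bias in the comparison with the IPI can be claimed. It depends on which form is used and on whether the cut was found in the data being analysed, and neither is stated.

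**What to change.** Amend three sections:
- **Model construction:** state that the R-signature enters the univariate and multivariable Cox models as a continuous linear predictor, and that its significance test is the Cox test of that score in the patients otherwise used for the log-rank test.
- **Model performance assessment:** state that the ROC, calibration and decision-curve steps use the continuous score, or the model containing it.
- **Radiomics feature selection:** state that the X-tile groups serve only to display Kaplan-Meier curves, with any log-rank P value marked as descriptive.

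This removes both the grouping loss and the effect of searching for a cut from the models. It does not remove optimism from testing the score in the patients used to fit its LASSO weights, which is a separate matter.

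The cost is a few sentences and no new data. The small downside is that the high/low groups no longer carry a formal P value.

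### If the integrated Cox model is fitted on data that include the LASSO training patients, it over-weights the R-signature and under-weights the IPI, and its significance rule cannot screen out a signature that adds nothing

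*Combined protocol and SAP*

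**What the plan says.** The aim (Objectives) is to "investigate whether the RS could improve the prognostic value of the IPI in predicting progression-free survival (PFS) and overall survival (OS") in DLBCL.

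Under Radiomics feature selection, an ICC filter is applied to "1248 features, including 3 conventional and 1245 radiomics features". LASSO Cox with 10-fold cross-validation then "was applied to select the optimal features with non-zero coefficients in the training set". The score follows: "The radiomics signature was developed by linear combination of the selected features weighted by their respective coefficients". A cut-off is added: "The cut-off value of the radiomics signature was identified by X-tile software".

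Under Model construction, the score is handled like any baseline covariate: "Univariate Cox regression analysis was performed to investigate the prognostic value of the R-signature and clinical variables". The next step is: "Then, all significant variables were enrolled into a stepwise multivariate Cox regression to build an integrated radiomics-based model for PFS and OS prediction".

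The plan does not say which patients are used for Model construction, or whether the signature enters as a continuous score or as high/low risk. It describes no out-of-fold score, offset, joint penalised fit or shrinkage of the final model. The 10-fold cross-validation belongs to the LASSO step. Under Model performance assessment, the bootstrap supplies only confidence intervals for the AUC, and the calibration plots and Hosmer-Lemeshow test assess the model without correcting it.

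**The concern.** The two main predictors do not start level. The IPI is a fixed score calculated without reference to these patients' outcomes. The signature is a sum of features chosen, and weighted, because they tracked the outcomes of the training patients. If the same patients enter the second Cox model, the chance part of that agreement is credited to the signature a second time. An unpenalised refit also undoes the shrinkage that LASSO applied. Where PET features correlate with the IPI, the signature takes over part of the IPI's effect as well.

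This bears directly on the study question. A mis-weighted equation can hide real added value in new patients, or predict worse than the IPI when there is no added value. Because entry depends on significance, a signature fitted to the same outcomes is almost certain to pass. The fault lies in how the model is built: a clean validation set could reveal it but would leave the equation as it is.

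**Working it through.** **No figure to reproduce.** The documents state no sample size, event count, split or expected effect. The check is therefore a simulation of the described sequence under stated assumptions.

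**Model.** Let S = Σ w_j x_j, with w from LASSO Cox (10-fold cross-validation) in the training patients. The integrated model is log hazard ratio = b_S·S + b_I·IPI. The coefficients from the training refit are compared with those for the same S and the IPI in 1500 new patients.

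**Inputs from the plan:** LASSO Cox with 10-fold cross-validation; a coefficient-weighted score; a Cox refit; two-sided P<0.05.

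**Assumptions:** 150 or 250 training patients; about 35–40% events; 800 features surviving the ICC filter; IPI log HR 0.5 per SD; radiomic log HR 0 to 1.0; some features correlated 0.4 with the IPI; 40 runs per scenario. Runs in which LASSO selected nothing were dropped (from 0 to 17 of 40 in the scenarios tabulated). Coefficients are medians and C-indices are means.

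| n | radiomic log HR | signature: training / new | IPI: training / new | C in new patients, IPI alone | C, refit as planned | C, weights from new patients | C, out-of-fold weights | refit worse than IPI |
|---|---|---|---|---|---|---|---|---|
| 150 | 0 | 0.74 / 0.01 | 0.29 / 0.49 | 0.634 | 0.582 | 0.636 | 0.630 | 100% |
| 150 | 0.3 | 0.96 / 0.12 | 0.20 / 0.59 | 0.666 | 0.620 | 0.669 | 0.665 | 97% |
| 150 | 0.6 | 1.17 / 0.31 | 0.21 / 0.59 | 0.691 | 0.667 | 0.703 | 0.696 | 89% |
| 150 | 1.0 | 1.95 / 0.63 | 0.09 / 0.54 | 0.708 | 0.717 | 0.745 | 0.740 | 33% |
| 250 | 0 | 0.65 / −0.01 | 0.23 / 0.52 | 0.637 | 0.596 | 0.638 | 0.637 | 100% |
| 250 | 0.3 | 0.90 / 0.13 | 0.18 / 0.56 | 0.666 | 0.632 | 0.670 | 0.667 | 100% |
| 250 | 0.6 | 1.21 / 0.41 | 0.14 / 0.53 | 0.691 | 0.684 | 0.710 | 0.706 | 62% |

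**Size of the mis-weighting.** At log HR 0.6 the signature weight is 1.17/0.31 = 3.8 times too large at n=150 and 1.21/0.41 = 3.0 times at n=250.

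**Entry rule.** The refitted signature had P<0.05 in 100% of non-empty runs, including those with no true signal. With out-of-fold values the null figure was 12–13%, which is still above 5% but rests on few runs.

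**Strong signal (n=150, log HR 1.0).** The gain available over the IPI is 0.745 − 0.708 = 0.037. The planned refit realises 0.717 − 0.708 = 0.009; out-of-fold weights realise 0.740 − 0.708 = 0.032.

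**Calibration slope in new patients (n=150).** 0.39 to 0.54 for the refit; 0.82 to 0.97 with out-of-fold weights.

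**Variations (n=150, log HR 0.6).**
- Fit in the whole cohort (70% training, 30% other): signature 0.93 vs 0.31, IPI 0.35 vs 0.59; C 0.681 against 0.690 for the IPI alone.
- Signature dichotomised at an outcome-optimised cut-off: 1.93 vs 0.42, IPI 0.39 vs 0.64.
- Features uncorrelated with the IPI: signature 0.91 vs 0.21, and a smaller IPI deficit, 0.36 vs 0.46.

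**Separately written simulations.**
- n=130, 1245 features (no ICC filter), real signal: signature 0.99 vs 0.37, IPI 0.43 vs 0.61. C was 0.686 for the IPI alone, 0.687 as planned and 0.710 with correct weights. With no radiomic information beyond the IPI, C was 0.652 as planned against 0.668 for the IPI.
- 600 features: signature 0.92 vs 0.00 under the null, and 0.87 vs 0.47 at n=250 with signal. Out-of-fold weights raised C from 0.572 to 0.636 and from 0.689 to 0.692 respectively. At n=250 the planned model beat the IPI alone.

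**The case against.** The strongest objection is that the plan ties only the LASSO step to the training set and names no set for Model construction. If the integrated model were fitted wholly in other patients, this fault would not arise. That stands, so the point is conditional. A whole-cohort fit would not escape it, as the variation above shows.

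Second, the simulated model is simpler than the planned one. The fits contain the signature and the IPI only; the univariate screen, the stepwise step and the other clinical variables were not simulated in the tabulated runs. A reader might infer that the IPI will drop out of the stepwise model. The nearest evidence is that the IPI was non-significant in 22% of two-variable training fits at n=130, which shows a risk and not the behaviour of the planned procedure.

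Third, a reader might suppose that LASSO searches all 1248 features. It sees only those passing both ICC thresholds, and that number is not given. Fewer candidates may mean less overfitting.

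Fourth, the remedy is imperfect. At n=150 and log HR 0.6, out-of-fold weights erred the other way: signature 0.16 against 0.31 in new patients, IPI 0.69 against 0.59. Discrimination still improved on the planned refit, from 0.667 to 0.696.

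**Conclusion.** The concern holds conditionally. If the fitting data include the LASSO training patients, the planned refit over-weights the signature and under-weights the IPI, and P<0.05 does not protect against a worthless signature. The direction held in every scenario, including whole-cohort fitting and dichotomisation.

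The size is illustrative. It rests on assumed sample sizes of 130 to 250, assumed event rates and feature counts, and an assumed true signal. With no or weak signal, the integrated model did worse than the IPI alone in new patients. With a moderate signal, results ranged from clearly worse (0.667 vs 0.691 at n=150) through slightly worse (0.684 vs 0.691 at n=250) to a small gain in another simulation at n=250. With a strong signal the model gained, but less than it could.

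Two stronger readings are not supported. One is that the published equation is certainly mis-weighted: the fitting set is not stated. The other is that added value over the IPI will be lost: that depends on sample size and signal. Confidence is medium; the change should be made, and stating the fitting set comes first.

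**What to change.** 1. State which patients are used to fit the integrated model, and whether the signature enters as continuous or dichotomised.
2. Keep the planned signature for its own Kaplan-Meier analysis. For the multivariable Cox, estimate the signature and IPI weights from out-of-fold signature values, repeating the whole LASSO within each fold, including its inner choice of penalty. If the signature is dichotomised, repeat the X-tile cut-off within each fold as well.
3. Force the IPI into the model. Judge added value from the out-of-fold score, not from the P value of the score in the patients who produced it.

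A single LASSO Cox with the IPI unpenalised, used directly as the integrated model, is an acceptable alternative if any other clinical variables to be kept are also entered unpenalised. Its benefit is less consistent: C was 0.707 against 0.687 as planned at n=130, but one simulation found no gain at n=250. Its feature weights are conditional on the IPI, so a separate stand-alone signature would still be needed.

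Cost: an outer cross-validation loop in the R software already in use, and no new data. The signature's hazard ratio and P value will be less favourable, and in small samples the signature may be somewhat under-weighted.

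### Nothing in the stepwise Cox rule keeps the IPI apart from its own five items or holds it in the model, so the integrated model need not be the IPI plus the R-signature

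*Combined protocol and SAP*

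**What the plan says.** The Objectives paragraph sets the question: to "investigate whether the RS could improve the prognostic value of the IPI in predicting progression-free survival (PFS) and overall survival (OS) in DLBCL".

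Under Study population, the recorded variables begin "Clinical variables including gender, age at diagnosis, cell of origin, performance status, B symptoms, Ann Arbor stage, serum lactate dehydrogenase level" and end "extranodal involvement and treatment regimens of each patient were recorded. The IPI score was calculated". Five of the variables listed there are age, performance status, stage, LDH and extranodal involvement. The IPI appears in its own sentence after the list.

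Under Model construction, the screening step reads "Univariate Cox regression analysis was performed to investigate the prognostic value of the R-signature and clinical variables". The next sentence gives the entry rule: "all significant variables were enrolled into a stepwise multivariate Cox regression to build an integrated radiomics-based model for PFS and OS prediction". The only significance limit, under Statistical analysis, is a two-sided P below 0.05.

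Under Model performance assessment, the AUC of the radiomics-based model is compared with that of the clinical variables. A comparison of IPI plus R-signature with IPI alone is not specified.

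The plan does not say whether the IPI is one of the clinical variables screened, how it or its items are coded, what the stepwise entry and removal limits are, or whether collinearity is checked.

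**The concern.** A question about adding to the IPI needs a model in which the IPI stays the IPI. The stated rule does not secure this. A composite and its parts may compete in one selection driven by P values. The IPI may drop out in favour of some of its items, or it may stay beside an item. In the second case its coefficient is collinear with that item's and no longer describes the standard score.

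What is at stake is attribution. If the integrated model outperforms the IPI, the reader will credit radiomics. Under this rule some of the improvement can come from giving the clinical items weights fitted to this cohort, which would be possible with no PET data at all.

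**Working it through.** **Inputs.** The documents give the variable list, the entry rule and the 0.05 limit. They give no sample size, event count, item coding or stepwise limits, so there is no figure of the plan's own to reproduce. The documents also do not define the IPI. It is assumed here to be a 0 to 5 count of the five variables named above, all of which are in the recorded list.

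**Step 1: what the text permits.**
- IPI and items both candidates: they compete in one selection.
- Items only: the integrated model has no IPI term.
- IPI only: its items are kept out, but the IPI can still be dropped by selection.

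No reading guarantees a model containing the IPI and the R-signature without IPI items.

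**Step 2: algebra.** Write IPI = x1 + x2 + x3 + x4 + x5, each x coded 0 or 1. If the IPI stays with item x1, the linear predictor contains

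b·IPI + d·x1 = (b + d)·x1 + b·(x2 + x3 + x4 + x5).

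This is a valid model, but it is a re-weighted index. The coefficient b is the weight of the other four items and not the effect of the standard score. The six columns (five items and their sum) have rank 5, so all six cannot be fitted together under this coding.

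**Step 3: how often selection does this.** Illustrative simulation, 300 runs per row. Assumptions: correlated binary items, signature HR 1.5 per SD, univariate screen at P<0.05, stepwise entry below 0.05 and removal above 0.10. Item HRs are all 1.6 (equal) or 1.3, 2.2, 1.3, 2.0, 1.3 (unequal).

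| Patients | Mean events | Item effects | IPI out | IPI kept with item(s) | Sum |
|---|---|---|---|---|---|
| 100 | 47.2 | equal | 9.7% | 9.7% | 19.4% |
| 100 | 45.5 | unequal | 23.3% | 16.0% | 39.3% |
| 150 | 71.4 | equal | 3.0% | 13.7% | 16.7% |
| 150 | 67.2 | unequal | 23.0% | 24.7% | 47.7% |
| 250 | 119.0 | equal | 0.0% | 19.7% | 19.7% |
| 250 | 113.6 | unequal | 12.3% | 54.3% | 66.6% |

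The IPI and at least one item both passed the univariate screen in 99% to 100% of runs. The sum adds two different outcomes: displacement and joint retention. With unequal effects it rises with sample size.

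**Step 4: does it affect the gain over the IPI?** A further simulation assumed 200 patients, about 55% with an event, unequal item effects and a signature with no effect. The IPI was dropped or joined by its items in about 61% of fits. The integrated model gained about 0.014 in C-index over the IPI although radiomics contributed nothing. With the items withheld, the gain was about 0.001 and the IPI stayed in every fit. So about 0.014 − 0.001 = 0.013 came from the items.

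**The case against.** The strongest reply is that the plan never names the IPI as a stepwise candidate. It sits in a separate sentence after the variable list, and the screening sentence does not mention it. This stands as a limit on the claim: candidacy is an inference from the objective and from the ordinary sense of clinical variables. It does not rescue the plan, because if the IPI is not a candidate the integrated model omits the index it is meant to improve.

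The second reply is that the signature's own coefficient barely moves. In a simulation with 200 patients, 45% events, a true log-HR of 0.3 and 100 runs per setting, the signature log-HR adjusted for the selected clinical terms differed from the log-HR adjusted for the IPI alone by a mean absolute 0.006 (equal item effects) or 0.013 (unequal), against a standard error of about 0.12. This also stands. The harm lies in the gain in discrimination credited to radiomics, as Step 4 shows, more than in the signature's hazard ratio.

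Third, a re-weighted clinical model can be a harder test for the signature than the IPI. That is true if it serves as the comparator. It is not true if the re-weighted items sit in the radiomics model and the IPI alone is the comparator.

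Four stronger readings are tempting and are not supported:
- That prognostic information is counted twice. Cox coefficients are partial, and Step 2 shows only a change of weights.
- That the model cannot be estimated. This needs all five items to pass the screen, be coded as in the score, and be fitted together with their sum. The documents state no coding, and a stepwise procedure need not fit all six terms.
- That the model could not be used in a clinic. Any clinic that calculates the IPI already holds the items.
- That the simulated percentages predict this study. They depend on assumed inputs.

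**Conclusion.** The concern holds in a limited form. The entry rule allows the IPI to be displaced by, or kept beside, the variables it is assumed to be built from, and no sentence fixes it in the model. The integrated model therefore need not answer whether the signature adds to the IPI. This is more than a missing detail, because the rule as stated admits every significant variable.

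The size cannot be fixed from the documents. Under the assumptions shown, the IPI was dropped or joined by its items in about 17% to 67% of fits (displacement alone 0.0% to 23.3%), and the gain unrelated to radiomics was about 0.013 in C-index with unequal item effects. When the items carry similar weight, there is less to gain from re-weighting them. A reader might infer that the plan expressly enters the IPI and all five items together. It does not: candidacy of the IPI is inferred, and items enter only if significant on their own. The conclusion also rests on the assumed five-item make-up of the IPI.

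**What to change.** Under Model construction:
- Enter the IPI as one fixed term (score 0 to 5), not subject to selection.
- Withhold age, performance status, stage, LDH and extranodal involvement from the multivariable step. Report them univariately, or in a separate sensitivity model that uses them in place of the IPI.
- Keep the R-signature, gender, cell of origin, B symptoms, β2-microglobulin and regimen as the other candidates.

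Under Model performance assessment, judge added value by IPI plus R-signature against IPI alone, for PFS and for OS, with a likelihood-ratio test and the difference in time-dependent AUC. Make this comparison whatever the stepwise step retains. In the training set the test will be optimistic, because the signature was selected on the same outcomes.

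The cost is a few sentences and a re-run on data already collected. Apparent fit may fall slightly, because the items are no longer re-weighted to this cohort.
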